6.13.1. Adverse Events

An overview of the number and percentage of patients with TEAEs, SAEs, death due to an AE, and discontinuations from study due to an AE will be summarized for the enrolled population using the LAS data set.

An overview of the number and percentage of patients with TEAEs, SAEs, death due to an AE, and discontinuation from the study or from study treatment due to an AE, as well as the relationship to study treatment (tirzepatide, insulin lispro [U100]) will be summarized by treatment for the SS data set.

A TEAE is defined as an event that first occurred or worsened in severity after baseline. The baseline of a TEAE for LAS is defined as prior to the first insulin glargine (U100) after Visit 2. The baseline of a TEAE for the SS data set is defined as prior to first dose of randomized study drug (tirzepatide or insulin lispro [U100]). The Medical Dictionary for Regulatory Activities (MedDRA) Lowest Level Term (LLT) will be used in the treatment-emergent derivation. The maximum severity for each LLT during the baseline period, including ongoing medical history, will be used as baseline severity. For events with a missing severity during the baseline period, it will be treated as ‘mild’ in severity for determining treatment-emergence. Events with a missing severity during the postbaseline period will be treated as ‘severe’ and treatment-emergence will be determined by comparing to baseline severity. For TEAEs after randomization, the summary will be provided by treatment.

The percentages of patients with TEAEs will be summarized using MedDRA PT nested within SOC. Statistical comparisons will be applied at both the SOC and PT levels. Events will be ordered by decreasing frequency within System Organ Class (SOC). For events that are sex-specific, the denominator and computation of percentages will include only patients from the given sex.

The percentages of patients with TEAEs, overall and common (common TEAEs occurred in $\geq 5\%$ of patients before rounding), will be summarized using MedDRA Preferred Term (PT). Events will be ordered by decreasing frequency.

The percentages of patients with TEAEs by maximum severity will be summarized using MedDRA PT. For each patient and TEAE, the maximum severity for the MedDRA PT is the maximum postbaseline severity observed from all associated LLTs mapping to the MedDRA PT. The maximum severity will be determined based on the non-missing severities. If all severities are missing for the defined postbaseline period of interest, it will be shown as missing in the table. Only counts and percentages will be included for the TEAEs by maximum severity.

Patient narratives will be provided for all patients who experience any of the following “notable” events:

- death
- serious adverse event, or
- permanent discontinuation of study treatment due to an AE.

A listing of AEs occurring after the patient’s last date of study participation will be provided using the SS data set. The listings will include patient identification including the treatment (for patients who are randomized), site number, and event information: AE group ID, event start date, MedDRA SOC, and PT, seriousness, severity, outcome, first dose date of insulin glargine (U100) and first and last dose date of the study drug (tirzepatide or insulin lispro [U100] for patients who are randomized).

6.13.1.1. Deaths

A listing of deaths will be provided using the SS data set. The listing will include patient identification including the treatment, site number, date of death, age at the time of enrollment, sex, associated AE group ID, time from first dose of study drug (tirzepatide/insulin lispro [U100]) to death, time from last dose of study drug (tirzepatide/insulin lispro [U100]) to death (if patient had discontinued study drug), cause of death as reported by the investigator, and cause of death as adjudicated by the clinical endpoint committee (CEC). If applicable, a separate listing of deaths will be provided for the insulin glargine (U100) optimization period using the LAS data set. The listing will include patient identification information.

6.13.1.2. Other Serious Adverse Events

The number and percentage of patients who experienced an SAE (including deaths and SAEs temporally associated or preceding deaths) during the treatment period and the follow-up period will be summarized by treatment using MedDRA PT nested within SOC. If applicable, the number and percentage of patients who experienced an SAE during the insulin glargine (U100) optimization period will be summarized using MedDRA PT for the LAS data set.

Listings of all SAEs will be provided. For the insulin glargine (U100) optimization period (Visit 2 to Visit 6), the listing will include insulin optimization group (Group 1A, Group 1B and Group 2), randomized (Yes/No), patient identification including the site number, date of the event, age at the time of enrollment, sex, AE group ID, MedDRA PT, severity, outcome, and time from first dose of insulin glargine (U100) to the event. For the treatment period including the follow-up period, the listing will include treatment, patient identification including the site

number, date of the event, age at the time of enrollment, sex, AE group ID, MedDRA SOC and PT, severity, outcome, relationship to study drug (tirzepatide or insulin lispro [U100]), time from first dose of study drug (tirzepatide or insulin lispro [U100]) to the event, and time from most recent dose to the event (if the patient discontinued study drug prior to the event).

6.13.1.3. Discontinuation from the Study due to an Adverse Event

The number and percentage of patients who prematurely discontinue the study due to an AE will be summarized by treatment using MedDRA PT nested within SOC for the treatment and follow-up period. Events will be ordered by decreasing frequency within SOC.

If applicable, the number and percentage of patients who prematurely discontinue the study due to an AE will also be summarized using MedDRA PT for the insulin glargine (U100) optimization period.

6.13.1.4. Discontinuation from Study Drug due to an Adverse Event

The number and percentage of patients who prematurely discontinue study drug due to an AE will be summarized by treatment using MedDRA PT nested within SOC. Events will be ordered by decreasing frequency within SOC. A time-to-event analysis will be conducted by treatment on time to study drug (tirzepatide or insulin lispro [U100]) discontinuation.

6.13.1.5. Treatment of Overdose

A listing of patients reporting over-dosing of tirzepatide will be provided.

6.13.2. Special Safety Topics

6.13.2.1. Hypoglycemic Events

Definitions of different categories of hypoglycemic events are included in [Table GPHD.6.3](#).

Table GPHD.6.3. Definitions of Hypoglycemic Event Categories

| | Symptoms and/or Signs of Hypoglycemia | Blood Glucose Level |
|--|---------------------------------------|------------------------|
| Glucose Alert Value (Level 1): | | |
| Documented symptomatic hypoglycemia | Yes | ≤70 mg/dL (3.9 mmol/L) |
| Documented asymptomatic hypoglycemia | No | ≤70 mg/dL (3.9 mmol/L) |
| Documented unspecified hypoglycemia | Unknown | ≤70 mg/dL (3.9 mmol/L) |
| Clinically Significant Hypoglycemia (Level 2): | | |
| Documented symptomatic hypoglycemia | Yes | <54 mg/dL (3.0 mmol/L) |
| Documented asymptomatic hypoglycemia | No | <54 mg/dL (3.0 mmol/L) |
| Documented unspecified hypoglycemia | Unknown | <54 mg/dL (3.0 mmol/L) |
| Severe Hypoglycemia (Level 3) | | |

Severe hypoglycemia: Defined as an episode with severe cognitive impairment requiring the assistance of another person to actively administer carbohydrate, glucagon, or other resuscitative actions. Severe hypoglycemia will be reported as an SAE.

Nocturnal hypoglycemia: Defined as any hypoglycemic event that occurs between bedtime and waking.

Severe hypoglycemia requiring hospitalization, documented medical help, or is life threatening: Defined as any severe hypoglycemic event that has one of the following records in the electronic case report form (eCRF):

- The hypoglycemia event required emergency room visit or initial/prolonged hospitalization.
- The patient could not treat themselves and received assistance from medical personnel such as an emergency medical technician, nurse or physician.
- The hypoglycemia event was treated with glucagon or intravenous glucose.
- The hypoglycemia event caused disability or permanent damage to the patient.
- The patient experienced seizure or loss of consciousness.
- The hypoglycemia event caused death or was life threatening and fatal.

To avoid duplicate reporting, all consecutive hypoglycemic events in the same category, defined in [Table GPHD.6.3](#), occurring within a 1-hour period may be considered to be a single hypoglycemic event. Severe hypoglycemia will be considered as adverse events of special interest (AESIs).

For selected categories of hypoglycemia (including severe hypoglycemia and level 2 hypoglycemia/severe hypoglycemia), statistical summaries and analyses will exclude hypoglycemic events occurring after initiation of a new antihyperglycemic therapy. Incidence as well as rate per year of exposure will be provided by treatment.

Statistical summaries and analyses for severe hypoglycemia requiring hospitalization, documented medical help or is life threatening will be conducted using the Safety Analysis Set.

The incidence of hypoglycemic event will be analyzed using logistic regression with treatment, baseline HbA1c category, country/pooled country, and baseline metformin use (Yes/No) as fixed effects. The baseline incidence of hypoglycemic event during the insulin glargine (U100) optimization period and insulin optimization group may be adjusted as fixed effects. The rate of hypoglycemic episodes per patient year may be analyzed using a generalized linear mixed-effects model assuming the number of hypoglycemic episodes follows a negative binomial distribution with the mean modeled using country/pooled country, baseline metformin use (Yes/No), baseline HbA1c category, and treatment as fixed effects. The logarithm of days during the active treatment period will be adjusted as an offset to account for possible unequal treatment duration of follow-up between patients. The treatment term will include the combined tirzepatide arm and insulin lispro (U100). The baseline incidence/rate of hypoglycemic event during the

lead-in period and insulin optimization group may be adjusted as fixed effects. A nonparametric empirical model may be used to analyze the rate of hypoglycemic episodes if the event rate is low.

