- **Severe hypoglycemia** is defined as an episode with severe cognitive impairment requiring the assistance of another person to actively administer carbohydrate, glucagon, or other resuscitative actions. These episodes may be associated with sufficient neuroglycopenia to induce seizure or coma. Blood glucose measurements may not be available during such an event, but neurological recovery attributable to the restoration of BG to normal is considered sufficient evidence that the event was induced by a low BG concentration.

All severe hypoglycemia episodes should be reported as an SAE.

Other hypoglycemia categories

- **Nocturnal hypoglycemia** is defined as any hypoglycemic event that occurs between bedtime and waking.
- **Severe hypoglycemia requiring hospitalization, documented medical help, or is life threatening**

If a hypoglycemic event meets the criteria of severe, it needs to be recorded as serious on the AE CRF and reported to Lilly as an SAE.

To avoid duplicate reporting, all consecutive BG values ≤ 70 mg/dL (3.9 mmol/L) occurring within a 1-hour period may be considered to be a single hypoglycemic event.^{24,25}

In each case of suspected or confirmed hypoglycemia, it is important that the event be properly categorized, the effect of the intervention be assessed, and the frequency of hypoglycemia be evaluated. The role of dietary changes and physical exercise (or any other contributing factor) in the development of an event should be established. The participant should receive additional education, if deemed appropriate. Please refer to Section 6.6.1. for guidance on management of increased hypoglycemia risk.

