10.4.2. Definition of Serious Adverse Event

If an event is not an AE per definition above, then it cannot be an SAE, even if serious conditions are met (for example, hospitalization for signs/symptoms of the disease under study, death due to progression of disease).

An SAE is defined as any untoward medical occurrence that, at any dose:

a. Results in death

b. Is life-threatening

The term 'life-threatening' in the definition of 'serious' refers to an event in which the participant was at risk of death at the time of the event. It does not refer to an event, which hypothetically might have caused death, if it were more severe.

c. Requires inpatient hospitalization or prolongation of existing hospitalization

- In general, hospitalization signifies that the participant has been admitted to hospital for observation and/or treatment that would not have been appropriate in the physician's office or outpatient setting. Complications that occur during hospitalization are AEs. If a complication prolongs hospitalization or fulfills any other serious criteria, the event is serious. When in doubt as to whether "hospitalization" occurred or was necessary, the AE should be considered serious.
- Hospitalization for elective treatment of a pre-existing condition that did not worsen from baseline is not considered an AE.

d. Results in persistent disability/incapacity

- The term disability means a substantial disruption of a person's ability to conduct normal life functions.

- This definition is not intended to include experiences of relatively minor medical significance such as uncomplicated headache, nausea, vomiting, diarrhea, influenza, and accidental trauma (for example, sprained ankle) which may interfere with or prevent everyday life functions but do not constitute a substantial disruption.

e. Is a congenital anomaly/birth defect

f. Other situations:

- Medical or scientific judgment should be exercised in deciding whether SAE reporting is appropriate in other situations such as important medical events that may not be immediately life-threatening or result in death or hospitalization but may jeopardize the participant or may require medical or surgical intervention to prevent one of the other outcomes listed in the above definition. These events should usually be considered serious.

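### In SAP 6.13.2.1 the life-threatening criterion for the medically serious subset of severe hypoglycemia, read literally, admits only deaths, contrary to the category's name and the protocol's definition

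*SAP*

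**What the plan says.** Protocol 8.3.6.1 lists, among its other hypoglycemia categories, "Severe hypoglycemia requiring hospitalization, documented medical help, or is life threatening". It gives no further criteria.

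SAP 6.13.2.1 supplies them by reference to the eCRF: "Severe hypoglycemia requiring hospitalization, documented medical help, or is life threatening: Defined as any severe hypoglycemic event that has one of the following records". Six records follow. The first, on the place of care, is "The hypoglycemia event required emergency room visit or initial/prolonged hospitalization". The second, on who helped, is "The patient could not treat themselves and received assistance from medical personnel such as an emergency medical technician, nurse or physician". The third, on what was given, is "The hypoglycemia event was treated with glucagon or intravenous glucose". The fourth is disability or permanent damage, and the fifth is seizure or loss of consciousness. The sixth is "The hypoglycemia event caused death or was life threatening and fatal".

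On the meaning of life-threatening, Protocol 10.4.2 lists it as a seriousness criterion separate from death and says that the term "refers to an event in which the participant was at risk of death at the time of the event".

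The category has its own output. The SAP states that "Statistical summaries and analyses for severe hypoglycemia requiring hospitalization, documented medical help or is life threatening" will be run on the Safety Analysis Set, which by Table GPHD.6.1 keeps data after a new antihyperglycemic medication is started. The same section says that the analyses of selected categories, severe hypoglycemia among them, leave out events after a new antihyperglycemic therapy.

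**The concern.** The sixth record is the only one that refers to life threat, and it adds fatality as a condition. One of the three limbs in the category's name is then not delivered by its own criterion. Under the protocol's meaning, a participant can be at risk of death and survive, and that event does not satisfy the sixth record.

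The list is operative. Item 6 of the SAP revision history (Section 3) reports removing one criterion from this same list because it was not sufficient on its own, so individual entries decide which events are counted. A programmer who follows the sixth record literally codes deaths only; one who follows the category name also codes non-fatal life threat. The prespecified definition should not leave that choice open.

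At stake is the count in one separately reported safety category in a comparison with basal-bolus insulin.

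**Working it through.** No sample size, power or alpha figure bears on this, and the plan states no number to reproduce. The check is of the logic of the rule.

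**Inputs.** Six records in SAP 6.13.2.1, any one sufficient. Call the first five R1 (emergency room or hospital), R2 (medical personnel), R3 (glucagon or intravenous glucose), R4 (disability or permanent damage) and R5 (seizure or loss of consciousness). Let D be death and L life-threatening in the sense of Protocol 10.4.2.

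**Step 1: the sixth record as written.** D or (L and D). If D is true the expression is true; if D is false both halves are false. It reduces to D, and L has no effect.

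**Step 2: the sixth record as the category name implies.** D or L.

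**Step 3: the whole rule under each wording.**
- As written: R1 or R2 or R3 or R4 or R5 or D.
- To match the name: R1 or R2 or R3 or R4 or R5 or D or L.

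**Step 4: non-fatal life-threatening events (L true, D false).** The five other records can combine in 2^5 = 32 ways. As written, the event enters whenever at least one of R1 to R5 is present: 32 − 1 = 31 combinations. It is left out in the one combination where none is present.

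**Step 5: all severe events.** Treating every death as also life-threatening, D and L have three joint states (neither, L only, both), giving 32 × 3 = 96 patterns. The two wordings classify exactly one differently: L true, D false, R1 to R5 all absent. These counts describe the rule. They are not event frequencies, and the documents give none.

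**Step 6: can that pattern occur?** The level 3 definition requires severe cognitive impairment and active help from another person. The helper need not be medically trained, and carbohydrate is one of the forms of help named. An episode treated at home by a lay person, without seizure or loss of consciousness, meets level 3 with R1 to R5 all absent. Every severe episode is to be reported as an SAE, so an investigator could judge it life-threatening under Protocol 10.4.2.

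**Step 7: where would that event still appear?** As level 3 severe hypoglycemia, as an SAE in the summary and listing of SAP 6.13.1.2, in a patient narrative (SAP 6.13.1) and as an AESI (SAP 6.13.2.1). If it happened after a new antihyperglycemic therapy, the severe-hypoglycemia analysis would exclude it by design and this category would miss it through the wording. It would then be in neither of those two analyses, but still in the adverse event outputs.

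**The case against.** The strongest reply is that the other five records do nearly all the work. An event that truly puts a participant at risk of death will usually bring an ambulance, glucagon, loss of consciousness or a hospital visit, and any one of these is enough. Protocol 10.4.2 also narrows the term: it excludes events that might have been fatal only had they been more severe, so a home-treated episode without seizure or loss of consciousness may seldom qualify. The closing words may simply be loose phrasing that joins two eCRF responses; the form is not in the documents, so this cannot be settled from them.

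Most of that stands. It limits the consequence but does not repair the rule, which still contradicts its own title.

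A reader might infer more: that non-fatal life-threatening events can never enter the category, that such events are lost to safety reporting, or that the wording favors one arm. The documents do not support any of these. Five routes into the category remain open to survivors. The events stay visible as severe hypoglycemia, SAEs and AESIs. Nothing in either document indicates how the left-out pattern would divide between arms: home treatment alone does not place an event in it, because a home-treated event that was not life-threatening is meant to be outside the category.

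**Conclusion.** The wording defect is real and its reach is narrow. Read literally, the sixth record covers only deaths, in conflict with the category name in both documents and with Protocol 10.4.2. The events affected are severe, non-fatal, life-threatening episodes with none of the other five records: one pattern of 32. How many would occur is unknown and may be zero; the documents give no expected count of severe events and no basis for estimating the share.

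Only this category's count on the Safety Analysis Set can change. No efficacy analysis, and so no type 1 error-controlled analysis, depends on it. The conclusion assumes that the derivation follows the text as written; if it follows the category name, the output would be right and only the text needs correcting. This is a minor correction, worth making because an operative definition should match its name.

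**What to change.** In SAP 6.13.2.1, delete the last two words of the sixth record, so that it covers a hypoglycemia event that caused death or was life-threatening, with life-threatening as defined in Protocol 10.4.2. Confirm which eCRF field holds that information and name it in the derivation. The documents show that severe events are recorded as serious on the AE form, but not that each seriousness criterion is a separate field.

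The cost is two words in the SAP plus the check of the source field and any matching change to the derivation. The category count can only stay the same or rise, and no other analysis is affected.

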9.4.4.1. Hypoglycemic Events

Incidence of documented symptomatic hypoglycemia events and severe hypoglycemia will be compared between the pooled cohort of tirzepatide doses and insulin lispro (U100) using negative binomial regression analysis. Selected safety analyses may be conducted excluding data after introduction of another antihyperglycemic therapy, for example, rescue therapy.

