| Figure GPHD.5.1. | Illustration of study design for clinical protocol I8F-MC-GPHD..... | 13 |
| Figure GPHD.5.2. | Flowchart to ascertain need for insulin glargine (U100) optimization..... | 15 |
| Figure GPHD.6.1. | Type 1 Error control strategy for primary and key secondary efficacy endpoints..... | 29 |

Table of Contents

| Appendix | | Page |
|-----------------|--|-------------|
| Appendix 1. | Searching Criteria for Adverse Events of Special Interest..... | 50 |

3. Revision History

The first version of the statistical analysis plan (SAP) was approved prior to First Patient Visit (FPV).

The second version is approved before the final database lock. The following represent major changes made for the second version:

1. Updated definition of analysis set. For consistency with SURPASS 1-5 trials, exclude patients discontinuing study drug due to inadvertent enrollment from efficacy analyses.
2. Updated baseline definition as time is not collected in GPHD eCRF.
3. Missing data imputation: Modified the definition of “retrieved dropouts”.
4. Updated analysis used for hemoglobin A1c (HbA1c) and weight loss threshold analyses.
5. Change in alpha recycling for type 1 error rate control.
6. Removed ‘The patient recovered/ resolved with sequelae’ from Severe hypoglycemia requiring hospitalization, documented medical help, or is life threatening as this criteria alone will not be sufficient to meet additional criteria.
7. Removed section on Anti-Drug Antibodies as it was not collected for all patients.
8. Added section to assess SARS-CoV-2 (COVID-19) impact.

4. Study Objectives

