6.2. General Considerations

Statistical analysis of this study will be the responsibility of Eli Lilly and Company (Lilly) or its designee. All statistical analyses will be conducted with SAS Version 9.4 or higher unless otherwise stated. Any change to the data analysis methods described in the protocol will require an amendment only if it changes a principle feature of the protocol. Any other changes to the data analysis methods described in the protocol, and the justification for making the change, will be described in the SAP or the clinical study report (CSR). Some analyses and summaries described in this analysis plan may not be conducted if not warranted by data (eg, few events to justify conducting an analysis). Listings of events will be provided in such situations. Additional analyses of the data may be conducted as deemed appropriate without further changes made to the protocol or SAP, even after the final database lock (DBL).

Additionally, to avoid potential selection biases, unless stated otherwise, statistical summaries and analyses will be conducted based on randomized maintenance dose regardless of the actual treatment received by the participants. In the event of a treatment error, participants will be analyzed according to the treatment they were randomized.

There will be 2 estimands of interest in evaluating the primary and secondary efficacy objectives. The first estimand, the “efficacy” estimand, represents efficacy prior to discontinuation of study intervention and without the confounding effects of rescue therapy for severe persistent hyperglycemia. Analyses relative to the “efficacy” estimand will be conducted using the efficacy analysis set (EAS). The second estimand, the “treatment-regimen” estimand, represents the efficacy irrespective of adherence to investigational product or introduction of rescue therapy for severe persistent hyperglycemia. Analyses relative to the “treatment-regimen” estimand will be conducted using the full analysis set (FAS).

Unless specified otherwise, safety analyses for the treatment and the follow up period will be conducted relative to the “treatment-regimen” estimand using the safety analysis set (SS).

Unless specified otherwise, analysis for the lead-in period will be conducted using the lead-in analysis set (LAS).

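### Does the SAP drop the protocol's comparison of documented symptomatic hypoglycemia and leave the level 2 results open to unequal glucose testing?

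*SAP*

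**What the plan says.** Protocol section 9.4.4.1: "Incidence of documented symptomatic hypoglycemia events and severe hypoglycemia will be compared between the pooled cohort of tirzepatide doses and insulin lispro (U100"), with negative binomial regression as the method. It gives no glucose threshold.

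SAP section 6.13.2.1 defines symptomatic, asymptomatic and unspecified events at level 1 (70 mg/dL or lower) and level 2 (below 54 mg/dL) in Table GPHD.6.3, and severe events at level 3. It then states which events are left out once a new antihyperglycemic therapy starts: "For selected categories of hypoglycemia (including severe hypoglycemia and level 2 hypoglycemia/severe hypoglycemia"). Two models follow:

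- Incidence: "The incidence of hypoglycemic event will be analyzed using logistic regression with treatment, baseline HbA1c category, country/pooled country, and baseline metformin use (Yes/No").
- Rate: "The rate of hypoglycemic episodes per patient year may be analyzed using a generalized linear mixed-effects model", assuming a negative binomial distribution. On exposure: "The logarithm of days during the active treatment period will be adjusted as an offset".

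Neither model sentence names a category of event. On departures from the protocol's methods, SAP section 6.2 says that the change "and the justification for making the change, will be described in the SAP or the clinical study report (CSR").

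The secondary composite (HbA1c below 7.0% without hypoglycemia) counts any confirmed glucose below 54 mg/dL or a severe event, with no symptom condition. Protocol section 8.1.2 and SAP Table GPHD.6.2 agree on this.

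**The concern.** Read quickly, a protocol *will* has become a SAP *may*, and the protocol's lead category is not in the SAP's list of named groupings. The SAP revision history (section 3) does not explain it. Its one hypoglycemia item removes a criterion "from Severe hypoglycemia requiring hospitalization, documented medical help, or is life threatening as this criteria alone will not be sufficient", which is a different matter.

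The missing category would be a useful one. Level 2 and the composite both count symptom-free low readings, so both depend in part on how often participants measure. Lispro titration uses pre-meal and bedtime values that the tirzepatide arms do not need for titration, and the models adjust for baseline factors and days, not for testing frequency. Symptomatic events depend less on the testing schedule, because participants in every arm are encouraged to measure when they feel symptoms (protocol section 6.6.1). Lower hypoglycemia is part of the trial's rationale, so a tirzepatide advantage that came partly from closer testing under lispro would be a misleading safety message.

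**Working it through.** The plan gives no figure for hypoglycemia. Its only design figures are the HbA1c power values, 80% per dose and 97% pooled. These recompute to 80.1% and 97.8%, and nothing here bears on them.

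**1. The texts side by side.**

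- The phrase that seems to list the analysed categories is the start of a data-exclusion rule. Its list is introduced by *including*, so it is open.
- The next sentence promises incidence and rate per year by treatment. It could be read as confined to those selected categories. The logistic-regression sentence further down carries no such limit and sits in the section that has just defined symptomatic events.
- Table GPHD.6.3 supplies both thresholds that the protocol leaves open. It also settles events with no symptom information, which have their own row ("Documented unspecified hypoglycemia | Unknown") and so are not symptomatic events.
- The protocol assigns a count model to *incidence*. The SAP splits this into logistic regression for incidence and a negative binomial model for rate. The optional wording fits SAP section 6.2, which allows analyses to be skipped when events are few, and the nonparametric fallback for low event rates in section 6.13.2.1.
- The revision history lists major changes from the first to the second SAP version. It is not a log of differences from the protocol, so its silence shows nothing about this point.

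**2. Readings per week implied by the rules.**

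Inputs: a weekly floor for every arm of three fasting readings and one four-point profile (protocol section 6.1.2.2); lispro adjusted twice weekly to Week 24, from the last three values, or two if only two exist, at each of three non-fasting times (section 6.1.2.2.2).

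- Floor: 3 + 3 = 6 if the profile's fasting value is one of the three, otherwise 7.
- Lispro: 3 + 3v, plus 1 if the floor is 7, where v is the number of values per time point per week.
- Values reused between adjustments: v = 2 gives 9 or 10 (9/6 = 1.50, 10/7 = 1.43); v = 3 gives 12 or 13 (12/6 = 2.00, 13/7 = 1.86).
- Fresh values at each of two adjustments, which the protocol does not require: v = 4 gives 15 or 16 (2.50, 2.29); v = 6 gives 21 or 22 (3.50, 3.14).
- Adjustment may fall to once weekly after Week 24. The highest case then averages (21 × 24 + 12 × 28)/52 = 840/52 = 16.2 a week, and 16.2/6 = 2.7.
- Non-fasting readings alone: 3 against 6 to 9 with reuse, a ratio of 2 to 3.
- Every arm also collects two 7-point profiles before three post-randomization visits, at most 2 × 7 × 3 = 42 readings. With reuse and a floor of 6, the 52-week ratios become (468 + 42)/(312 + 42) = 1.44 and (624 + 42)/(312 + 42) = 1.88.

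All of these are readings of the rules. The floor is a minimum, and actual counts are unknown.

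**3. What that could do to a rate ratio.**

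Assume no true difference, and let s be the share of tirzepatide-arm level 2 events found only by routine readings. The documents give no s. If each extra reading has the same yield as a floor reading, the tirzepatide:lispro rate ratio is 1/((1 − s) + s·k), where k is the reading ratio. The share of lispro events that the extra readings would have to prevent to cancel the effect is 1 minus that.

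| s | k = 1.4 | cancelled by preventing | k = 2.0 | cancelled by preventing |
|---|---|---|---|---|
| 5% | 0.98 | 2.0% | 0.95 | 4.8% |
| 10% | 0.96 | 3.8% | 0.91 | 9.1% |
| 25% | 0.91 | 9.1% | 0.80 | 20.0% |

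Prevention is plausible, because low readings trigger lispro dose decreases (section 6.1.2.2.2). The sign of the net effect is therefore not established.

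**The case for a change.** The best case for a change is that a committed comparison should not have to be inferred. The protocol names a category and a method. The SAP, which is what gets programmed, names neither as firm, and one sentence would settle it using episode data already entered in the eCRF (protocol section 8.3.6.1). The wording mismatch stands, and so does the fact that lispro titration can use more non-fasting readings than the shared floor.

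The rest is weaker. No breach of SAP section 6.2 can be shown, because that section also allows a departure to be explained in the clinical study report. The symptomatic comparison would not isolate a testing effect: a documented symptomatic event still needs a measured glucose, and in an open-label trial symptom reporting brings its own bias. A gap between the symptomatic and level 2 rate ratios could reflect reporting as easily as sampling. A symptomatic version of the composite would be an optional extra beside an endpoint that follows the protocol and lies outside type 1 error control. A table of testing frequency may not be possible, since the protocol does not show that all routine readings reach the database.

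**Conclusion.** No change is called for. The SAP leaves a detail unstated: it defines documented symptomatic hypoglycemia and gives models that can be applied to it, without naming that comparison. The protocol names it, and nothing in the SAP withdraws it. An analyst working from both would run it at the two thresholds in Table GPHD.6.3, with unspecified events kept separate.

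The testing imbalance is real on paper, about 1.4 to 2.0 times in total weekly readings with reused values and higher only if fresh values are assumed. Its effect on hypoglycemia rates is unknown in size and sign. Following the documents as written does not lead to a result shown to be wrong, and no primary or key secondary test is involved.

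This rests on three assumptions: the protocol commitment is honoured, symptom status is recorded with each episode as the protocol requires, and any deliberate departure is explained in the SAP or the clinical study report.
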